10.3. Adverse Events of Special Interest

Adverse events of special interest (AESI) are pruritus, and dyslipidaemia. For each of these AESI, subject incidence of TEAEs and the total number of entries by MedDRA system organ class and preferred term will be presented. In addition, for each AESI, the time to first onset and time to most severe event will be summarized using descriptive statistics.

10.3.1. Pruritus

Treatment-emergent pruritus, defined as any preferred term including “Prur,” will be summarized separately by the MedDRA system organ class (SOC), treatment group, and preferred term (PT) as a subset of all TEAEs.

An analysis of treatment-emergent pruritus event days per patient years on study will be performed. The days at each severity grade, including the total days of event, the total patient years on study, and the event days per patient year on study at each severity grade, including the total, will be summarized. Each individual patient year on study will be derived as the last known date during the study minus the first dose date plus 1 divided by 365.25 days/year.

In order to explore the relationship between pruritus and the investigational product, the following time-to-event analyses will be performed:

- Time to first onset of treatment-emergent pruritus
 - The time to the start of the first episode will be calculated by date of onset of first episode – date of first dose of investigational product + 1.

Subjects who never report an AE of pruritus will be censored at the date of last contact.

- Time to onset of the first severe treatment-emergent pruritus
 - The time to the start of the first serious pruritus will be calculated by date of onset of the first severe pruritus – date of first dose of investigational product + 1.
 - Subjects who never report a severe AE of pruritus will be censored at the date of completion or discontinuation.
- Time to resolution of the most severe treatment-emergent pruritus event
 - The time to resolution of the most severe event of treatment-emergent pruritus will be calculated by date of resolution of the most severe event of treatment-emergent pruritus – start date of the most severe event of treatment-emergent pruritus + 1.
 - Subjects whose most severe event of treatment-emergent pruritus is ongoing will be censored at the date of completion or discontinuation. For subjects that are lost to follow-up, the last contact date will be used.
 - Only subjects that report a pruritus event are included in this analysis.
 - Separate summaries will be presented for those who discontinue due to pruritus.

The analysis of time to event will include the number of subjects with the event (first onset, first moderate or severe, first severe), the number of subjects without the event (censored), descriptive statistics of time for those with an event, and range in days for all subjects. Kaplan-Meier (KM) estimates will be calculated by treatment group. The quartiles, including the median time-to-event and their respective 2-sided 95% CIs, will be presented. KM estimates will be plotted as a “survival curve” for each treatment group, with the number at risk identified. The comparison of OCA to placebo will be summarized using a log-rank test stratified by randomization strata factor. The analysis will be repeated on the subset of subjects who experienced a treatment-emergent pruritus event.

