### **Pruritus**

Pruritus is a common symptom in PBC but less common in PSC ([Chapman 2011](#)). Investigator guidance for pruritus management strategies are outlined in [Section 11.1.3.1](#) of this protocol. Subjects who experience one or more episodes of severe pruritus that are not tolerable based on Investigator assessment, despite optimal supportive treatment as outlined in [Section 11.1.3.1](#), should be discontinued from the trial.

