**Table 9: Severity of Pruritus**

Pruritus Grade	Clinical Description of Severity for Pruritus	Titration Eligibility Guideline
1 = Mild	Generally localized; causing no limitation of usual activities or minimal sleep disturbance; the subject may experience slight discomfort. Medicinal intervention is not indicated.	Yes
2 = Moderate	Intense or widespread; causing some limitation of usual activities or sleep disturbance; the subject may experience annoying discomfort. Medicinal intervention may be indicated.	Yes; use clinical judgment
3 = Severe	Intense or widespread and interfering with activities of daily living (ADL), ie, causing inability to carry out usual activities, or severe sleep disturbance; the subject may experience intolerable discomfort. Medicinal intervention is typically indicated.	No

In the phase 2 PBC trials, Investigators tried a number of different approaches to help relieve pruritus symptoms. Severe pruritus typically appears to occur shortly (ie, within the first 2 weeks after starting therapy). In the 747-202 trial, about 80% of the patients who were started on BAS or other drugs or interventions during the trial completed the trial as planned. In the Phase 3 trial, similar approaches were employed in addition to evaluation of lower doses: 27% of subjects in the 10 mg group added a BAS compared to 20% of subjects in the titration arm and 11% of placebo subjects. Consistent with the use of lower doses and pruritus mitigation strategies withdrawals due to pruritus were minimized (1 subject in the titration arm and 7 in the 10 mg OCA arm withdrew due to pruritus compared to none in the placebo arm).

Since pruritus is such a subjective symptom (and the most common symptom in PBC patients), clinical judgment needs to be applied to the management of each subject. However, the following recommendations are made for the management of subjects experiencing significant pruritus in this PSC trial:

- Prescribe BAS, eg, cholestyramine, colestipol, colestimide, or colesevelam. The greatest experience to date has been with cholestyramine. Theoretically, colesevelam may be more palatable (tablet) and more effective. Patients taking BAS should be instructed to stagger their dosing of investigational product and UDCA ensuring at least 4 hours between doses of the BAS and investigational product (and UDCA).

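### Time to resolution of the most severe pruritus is censored at discontinuation, which can itself be caused by that pruritus, so Kaplan-Meier can overstate resolution on treatment; the SAP does not state the target that fixes the direction

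*SAP*

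**What the plan says.** SAP 10.3.1 measures the time from the start of a subject's most severe treatment-emergent pruritus event to its resolution. On the risk set: "Only subjects that report a pruritus event are included in this analysis". On events that have not resolved: "Subjects whose most severe event of treatment-emergent pruritus is ongoing will be censored at the date of completion or discontinuation"; for subjects lost to follow-up the last contact date is used instead. It adds: "Separate summaries will be presented for those who discontinue due to pruritus", without giving their content.

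For the time-to-event analyses of pruritus, "Kaplan-Meier (KM) estimates will be calculated by treatment group", with quartiles and plotted curves, and "The comparison of OCA to placebo will be summarized using a log-rank test stratified by randomization strata factor". No competing-event estimate or sensitivity analysis is specified. The purpose is exploratory: "In order to explore the relationship between pruritus and the investigational product, the following time-to-event analyses will be performed".

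Protocol 7.4.2, under Pruritus, names the subjects concerned: "Subjects who experience one or more episodes of severe pruritus that are not tolerable based on Investigator assessment", after the supportive measures of 11.1.3.1 have been tried. They are to leave the trial.

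**The concern.** Kaplan-Meier and the log-rank test assume that a subject censored on a given day would have gone on to resolve at the same rate as those still under observation. Protocol 7.4.2 makes that hard to accept, because a subject can be censored precisely because the itch would not settle. Removing slow resolvers from the risk set leaves the faster ones to represent them.

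Such withdrawals may also be uneven across arms. On the Phase 3 PBC trial, Protocol 11.1.3.1 reports: "1 subject in the titration arm and 7 in the 10 mg OCA arm withdrew due to pruritus compared to none" on placebo. If that pattern carried over, OCA-associated itch could look more self-limiting than it is while subjects remain on drug. Safety is a primary objective and pruritus is an adverse event of special interest (SAP 10.3), so the tolerability picture matters in a dose-finding trial.

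**Working it through.** **1. Plan's own figure.** There is none. The documents give no pruritus, resolution or withdrawal rate for PSC and no precision for this analysis. All rates below are assumptions.

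**2. What Kaplan-Meier adds relative to a cumulative incidence.** Take a constant resolution hazard r = ln 2 / median and a constant hazard w of withdrawal with itch ongoing. Choose w so that the stated share has withdrawn unresolved by day 112. Then

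- 1 − KM = 1 − exp(−r·t)
- cumulative incidence of resolution before withdrawal = r/(r+w) × [1 − exp(−(r+w)·t)]

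Example with a 60-day median and 10% withdrawing: r = 0.01155, w = 0.00171, t = 112. 1 − KM = 1 − exp(−1.294) = 72.6%. Cumulative incidence = (0.01155/0.01326) × [1 − exp(−1.485)] = 0.871 × 0.773 = 67.4%. The gap is 5.2 points.

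| Withdraw with itch ongoing | 60-day median: 1−KM / incidence / gap | 30-day median: 1−KM / incidence / gap |
|---|---|---|
| 5% | 72.6 / 70.0 / 2.6 | 92.5 / 88.5 / 4.0 |
| 1 of 15 (6.7%) | 72.6 / 69.1 / 3.5 | 92.5 / 87.2 / 5.3 |
| 10% | 72.6 / 67.4 / 5.2 | 92.5 / 84.5 / 8.0 |
| 15% | 72.6 / 64.7 / 7.9 | 92.5 / 80.4 / 12.1 |

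In this model the two hazards are independent, so Kaplan-Meier is unbiased for resolution had nobody withdrawn. The gaps are the distance between two target quantities, not bias from informative censoring.

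For scale, suppose 15 pruritus subjects in an arm (60% of 25, an assumption). At 15% withdrawal the simple binomial standard errors are √(0.647×0.353/15) = 12.3 points and √(0.804×0.196/15) = 10.2 points. The gaps are about 0.6 and 1.2 standard errors.

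**3. Censoring that does depend on the outcome.** Simulation with 400,000 subjects per scenario, read at day 84. Assumptions: 60% fast resolvers (median 28 days) and 40% slow (median 168 days); only slow resolvers still itching withdraw, between days 7 and 42; administrative censoring falls between days 60 and 160. True on-treatment resolution is 0.6 × (1 − 2^(−84/28)) + 0.4 × (1 − 2^(−84/168)) = 0.525 + 0.117 = 64.2%.

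| Realised itch withdrawal | 1−KM under the SAP rule | Incidence before withdrawal |
|---|---|---|
| 0% | 64.1 | 64.1 |
| 4.6% | 65.6 | 63.3 |
| 9.1% | 66.9 | 62.2 |
| 18.1% | 70.5 | 60.3 |
| 27.0% | 75.5 | 58.4 |

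1 − KM exceeds the on-treatment truth by about 1 to 11 points and the competing-event incidence by about 2 to 17.

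**4. If the target is resolution on or off drug.** Same model, with 10% or 20% of subjects assigned to withdraw. After stopping, the itch clears with an assumed median of 7, 14, 28 or 84 days.

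- Off-drug medians of 7 to 28 days, every withdrawal censored at discontinuation: truth 69.6 to 78.3%, KM 66.8 to 70.5%. KM *understates* by about 3 to 8 points.
- Same medians, clearances within the four-week follow-up counted and the rest dated back to discontinuation: KM 69.4 to 78.0%, within about 1 point of truth.
- Off-drug median of 84 days under that dated-back rule: KM 68.3 and 73.2% against truth 66.9 and 69.7%, an overstatement of 1.4 and 3.5 points.
- Clearances counted and the rest censored at the follow-up visit: 66.7 and 69.8% for the 84-day median, within 0.2 points of truth. For medians of 7 to 28 days it runs 0.3 to 1.9 points low.

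**The case against.** The strongest reply is that SAP 10.3.1 sets no on-treatment condition. It times the event to its resolution date, and resolution after stopping can be observed. Early terminators return four weeks after dosing ends, with adverse events assessed (Protocol 8.6.12). Adverse events are collected to the end of participation (11.1.4.1) and followed until they settle or the subject is lost (11.1.8). The drug-holiday guidance in 11.1.3.1 expects itch to subside off drug. A subject whose itch clears by the follow-up visit may never be censored. This stands, and it is why the direction is conditional. It also exposes a gap: the SAP does not say whether discontinuation means product, double-blind phase or trial, or whether clearances in follow-up count.

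Second, these subjects will be visible elsewhere: in the separate summaries, in the tables of adverse events leading to withdrawal (SAP 10.2), and in the pruritus event-days analysis. That is true, but disclosure does not correct the curve.

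Third, the analysis is exploratory, uses a post-randomization subset of arms of 25, and lies outside the multiplicity hierarchy (SAP 6.2.7). The bracketed event list in the Kaplan-Meier paragraph names only onset events, so applying the log-rank test to resolution is the likely reading, not an explicit one. This stands, and it limits the importance of the point.

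A reader might infer from the PBC counts that OCA arms here will lose many subjects to itch. The counts do not support that. Arm sizes are not given, so no rate follows. Seven of the eight withdrawals came from an arm that started at 10 mg, which this trial lacks; the 5-to-10 mg titration strategy it adopts (Protocol 4.6.2) had one. Protocol 7.4.2 describes pruritus as less common in PSC than in PBC, although 4.5 expects a similar dose-related exacerbation.

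**Conclusion.** The censoring is tied to the outcome, and Kaplan-Meier can overstate on-treatment resolution. It can also overstate when follow-up clearances count but subjects still itching are dated back to discontinuation, as in the run with slow off-drug clearing. It can understate when the target is resolution on or off drug and all withdrawals are censored at discontinuation.

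The size cannot be derived from the documents. With assumed itch-related withdrawal of about 5 to 15%, the gap between 1 − KM and cumulative incidence is a few points, up to about 12. That rests on assumed resolution medians and, for the upper end, on constant independent hazards.

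A reader might conclude that the rule definitely flatters OCA, or apply the planned 20% dropout and quote larger gaps. Neither is supported. The direction depends on an unstated target, the 20% is all-cause dropout in the sample-size section, and a zero gap on placebo would be a further assumption. The primary ALP conclusion is unaffected. This is a minor point with a cheap improvement.

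**What to change.** In SAP 10.3.1, for time to resolution of the most severe pruritus:

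1. Beside the Kaplan-Meier output, report the Aalen-Johansen cumulative incidence of resolution before discontinuation. Treat permanent discontinuation with pruritus ongoing as a competing event, and show that event's own cumulative incidence by arm. Censoring at completion of the double-blind phase is administrative and can stay.
2. For resolution regardless of treatment, count resolutions recorded through the four-week follow-up, and censor subjects still itching at their last adverse-event assessment instead of at discontinuation. State which discontinuation is meant.
3. Keep the between-arm comparison for this endpoint descriptive.

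The cost is a few lines of SAP text and one more exploratory output in a small post-randomization subset, with a possibly less favourable figure for OCA. Item 2 treats resolved and unresolved subjects alike but is not exact: in the runs above it was up to 1.9 points low when itch cleared quickly off drug.

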## 6. INVESTIGATIONAL PLAN

### 6.1. Overall Trial Design

#### *Double-blind phase (DB)*

This is a Phase 2, randomized, double-blind, placebo-controlled, dose-finding evaluation of the efficacy and safety of OCA in subjects with PSC. The trial design is shown in [Figure 1](#) and the schedule of trial procedures for the DB phase is presented in [Table 1](#). Approximately 75 subjects who provide written informed consent and meet all of the inclusion and none of the exclusion criteria will be randomized to 1 of 3 treatment groups as follows: 1.5 mg titrating to 3.0 mg OCA, 5 mg titrating to 10 mg OCA, or placebo in a 1:1:1 ratio. Subjects will administer investigational product orally, once daily for 2 consecutive 12-week periods.

For the first 12 weeks after randomization, the subject's dose will be 1.5 mg OCA, 5 mg OCA, or placebo. After 12 weeks, the subject's dose will be titrated as detailed in [Section 6.4.1](#) and DB treatment will continue for a further 12 weeks at that dose.

Randomization will be stratified by the presence or absence of concomitant UDCA use and total bilirubin level ( $\leq 1.5x$  ULN or  $>1.5x$  ULN but  $<2.5x$  ULN).

[figure not shown]

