**6.3. Treatment Assignment**

Eligible subjects will be randomized to 1 of 3 treatment groups and will initiate treatment with 1.5 mg OCA, 5 mg OCA, or matching placebo. Randomization will be in accordance to a 1:1:1 ratio (ie, 25 subjects/group).

Subjects will be stratified by the presence or absence of concomitant UDCA use and total bilirubin level at Screening, according to defined stratification criteria ([Section 8.4.1](#)) and then randomized in equal proportions to each of the treatment groups.

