10. SAFETY ANALYSES

All safety analyses will be based on the Safety Population. The evaluation of the effects of OCA on safety parameters in the PSC population is a primary objective of this study.

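### Repeating the pruritus log-rank comparison only in subjects who had pruritus removes the incidence difference and can hide, or sometimes reverse, OCA's main known harm

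*SAP*

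**What the plan says.** SAP 10.3.1 introduces three pruritus analyses (time to first onset, time to first severe event, time to resolution of the most severe event) with this purpose: "In order to explore the relationship between pruritus and the investigational product, the following time-to-event analyses will be performed".

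The main analysis keeps every treated subject. SAP 10 states: "All safety analyses will be based on the Safety Population". For first onset, "Subjects who never report an AE of pruritus will be censored at the date of last contact". Kaplan-Meier estimates by treatment group follow, and "The comparison of OCA to placebo will be summarized using a log-rank test stratified by randomization strata factor".

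The section then adds: "The analysis will be repeated on the subset of subjects who experienced a treatment-emergent pruritus event". It gives no reason for the repeat, no caveat and no rule for reading it against the main result. For time to resolution the restriction is already part of the definition: "Only subjects that report a pruritus event are included in this analysis".

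**The concern.** Whether a subject has pruritus is known only after randomisation and is itself affected by treatment. Protocol 4.5 reports a dose-dependent worsening of pruritus with OCA in PBC and expects similar results in PSC.

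For first onset, everyone in the subset has the event. Nobody is left event-free, so the test can compare only how early the cases in each arm began. An arm with many extra but later cases looks better than an arm with few early ones. For first severe pruritus, the subset compares the share of cases that become severe, which falls if OCA adds mostly milder cases.

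Safety is a primary objective and SAP 10.3 makes pruritus an event of special interest. The repeat would put a second p-value on that harm, unadjusted under SAP 6.2.7, which does not answer the question the section poses.

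**Working it through.** **No plan figure to reproduce.** The documents state no pruritus rate, hazard ratio or power for PSC. Taken from them: 25 subjects per group (Protocol 6.3); 24 weeks of treatment, since "Subjects will administer investigational product orally, once daily for 2 consecutive 12-week periods" (Protocol 6.1); a dose increase at Week 12 in both OCA groups but not on placebo (Protocol 6.4.1). Pruritus rates and timing below are assumptions. The calculations compare one OCA arm with placebo and are unstratified.

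**Step 1: mechanism, one fixed example.** Placebo has 6 cases out of 25, at weeks 1 to 9. OCA has 15 out of 25: 6 at nearly the same early times and 9 after Week 12. With O and E the observed and expected OCA events and V the hypergeometric variance, z = (O − E)/√V and the one-step HR is exp[(O − E)/V].

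- All subjects: O = 15, E = 10.01, V = 5.20. z = 4.99/√5.20 = +2.19, p = 0.029, HR = exp(4.99/5.20) ≈ 2.6. OCA is worse.
- Cases only: O = 15, E = 18.89, V = 1.66. z = −3.89/√1.66 = −3.01, p = 0.003. OCA looks protective, because median onset is 4 weeks on placebo and 13 on OCA.

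The data are the same; only the 19 placebo and 10 OCA subjects without pruritus have been removed.

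**Step 2: how often, first onset.** Assume 25 per arm and 32% background pruritus in both arms, spread evenly over 24 weeks. OCA has a further 36%, so expected cases are 0.32 × 25 = 8 on placebo and 0.68 × 25 = 17 on OCA. Only the timing of the extra cases changes.

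| Extra OCA cases occur in | Subset points the wrong way | Significantly wrong |
|---|---|---|
| Weeks 0–4 | 9% | 0.1% |
| Weeks 0–24 | 51% | 3% |
| Weeks 12–16 | 40% | 6% |
| Weeks 12–24 | 80% | 21% |

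Across these scenarios the all-subject test finds significant harm in about 64% to 82% of trials and the subset test in about 1% to 25%. In both ranges the low end belongs to weeks 12–24 and the high end to weeks 0–4. Repeat runs move the entries by up to about 3 points.

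**Step 3: proportional hazards.** With a constant HR of 2.5 (incidence 30% and 59%), the all-subject median HR is 2.47 and harm is detected in 56% of trials. In the subset the median HR is 1.12 and harm is detected in 5%. The signal is lost, not reversed.

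**Step 4: first severe pruritus.** Assume any pruritus in 20% (placebo) and 60% (OCA), severe in 8% and 16%, with the same timing in both arms. The severe share among cases is 8/20 = 40% on placebo and 16/60 = 27% on OCA. The all-subject median HR is 2.05; the subset's is 0.61, significantly wrong in 12% of trials. If OCA instead raises the severe share from 20% to 40% (any 30% and 70%, severe 6% and 28%), the subset HR is 2.09 and does not reverse.

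**The case against.** The best defence is that the repeat is supplementary. The all-subject analysis comes first and is valid. Beside it stand incidence by treatment group, event days per patient-year by severity, maximum severity, and the VAS and 5-D comparisons. A reader would see any higher OCA incidence next to the subset result. No decision rule depends on the repeat, and SAP Appendix A lists one table for each pruritus time-to-event analysis and none for the subset. All of this stands, and it limits the severity.

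A reader might infer that the Week 12 dose increase makes a reversed result likely. The documents do not support that. Their only onset evidence, in Protocol 11.1.3.1, is that severe pruritus in the PBC trials typically came within two weeks of starting therapy. It concerns severe itch in another disease, but it is closest to the weeks 0–4 row, where reversal is rare. Cases clustered soon after titration (weeks 12–16) do not reverse systematically either; the 80% figure needs late cases dispersed to Week 24. The same section also advises against titrating subjects who have had severe pruritus.

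It is also fair that onset timing among cases is a legitimate descriptive question, and that for time to resolution the sentence changes nothing. The objection does not rescue the between-arm test in the subset: in every first-onset scenario above it says less about harm than the test already planned.

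**Conclusion.** The point holds in limited form. For time to first onset and time to first severe pruritus, the event-only repeat is not a randomised comparison and cannot serve the section's stated aim. Its usual effect is to lose the harm signal. Reversal can occur, but needs dispersed late OCA onsets or, for severe pruritus, OCA cases that are mostly non-severe. The percentages rest on assumed rates and timing, so they show a range and do not forecast this trial.

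It would go too far to conclude that the pruritus evaluation as a whole is compromised: the all-subject test, the incidence tables and the primary ALP analysis are untouched, and time to resolution is limited to cases by definition. This is a minor point and a free improvement.

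**What to change.** In SAP 10.3.1, restrict the repeat sentence. For time to first onset and time to first severe pruritus, remove the between-arm log-rank test and Kaplan-Meier comparison in the event-only subset. Present onset times among cases descriptively by arm, next to the incidence of pruritus and the all-subject Kaplan-Meier curves. Time to resolution needs no change.

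The cost is one edited sentence. No table listed in Appendix A is lost, and the section already plans descriptive times for subjects with an event. SAP 10.3.2 sets out nearly the same time-to-event plan for dyslipidaemia without such a repeat.
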